4.12. Deep learning model development

The above methods are utilized to create the same train, development, test dataset with patients identically coded into those groups to allow for direct comparison. The first set of models generated utilize only tabular data and are based off of neural accumulators (NAC) and neural arithmetic logic units (NALU).²⁰ NACs/NALUs are neural layers designed to learn functions comprised of arithmetic expressions such as addition, subtraction, multiplication, and division. The most promising aspect of NAC/NALU is that by learning generalizable numerical representations, there is hope to build neural networks that are explainable with simple and sparse arithmetic of raw input features. This architecture's inductive bias is dependent upon learning a set of weights which, after some internal operations, yield values near -1, 0, or 1. We have developed a modification of NAC/NALU to decrease overfitting and improve sparsity, believing this would lead to the model to output a simpler equation utilizing fewer features and less variance. To encourage this behavior, we appropriately parameterized Laplace priors on our weights. We refer to these layers as Laplacian-regularized NAC and NALU (LR-NAC, LR-NALU). From there, we plan to include the raw ECG waveform data in the NAC/NALU models as well as develop a convolutional neural network (CNN) model based primarily of the waveform data as discussed in Aim 2. The CNN model will be developed similarly using the

same train/dev/test splits. We will utilize the Adam optimizer and binary cross entropy as the loss function. We will assess convolutions across a single lead as well as a pooled convolution across all leads. We will then evaluate performance characteristics of the model with probability thresholds of 1%, 5%, 10%, 20%, 50%, and 75%.

2.6. Anticipated problems and strategies: Limited subject recruitment: We will continue to recruit patients until we have been able to successfully enroll 100 patients. We believe the recruitment pool of over 100,000 patients receiving an echocardiogram in the past eight years will allow for successful recruitment. False positive or negative amyloid scintigraphy scanning with planar imaging: ^{99m}Tc-PYP scanning has been found to have high levels of accuracy compared to biopsy in a large multicenter study which included patients seen at CUIMC.¹⁴ Additionally, we will use SPECT imaging which further reduces the risk of false positive testing.²¹ Identification of other types of amyloidosis: Every patient enrolled will undergo monoclonal protein testing to rule out AL amyloidosis and will have a clinical evaluation of assess for the risk of rare types of amyloidosis.

2.7. Aim 2: To incorporate additional data to improve the ability of deep learning models to predict cardiac amyloidosis

2.8. Rationale: Because current therapy for ATTR-CA only prevent disease progression without significantly reversing end-organ damage that has already occurred, it is imperative to attempt to diagnose patients as early as possible in their disease course. However, because the symptoms and structural changes of cardiac amyloidosis are more apparent in late stage disease, it is far more common for the diagnosis to be made in its later stages. In its current form, our deep learning model works incorporates many markers of advanced disease like decreased ECG voltage and increased LV wall thickness. As a result, in the same manner that diagnosis of ATTR-CA is easier with a more extreme phenotype in traditional clinical care, it is likely that our current model will have this same weakness. We believe the incorporation of additional clinical data and raw ECG waveform may improve the ability to detect patients at earlier stages of the disease and with less pronounced cardiac manifestations.

[figure not shown]
	Demographics Age Gender Orthopedic manifestations Carpal tunnel syndrome Spinal stenosis Joint replacement Tendon rupture
	Testing for Novel Clinical Associations New diagnosis associations? Predictive temporal symptom patterns? Suggestive vital sign patterns?

Figure 4: Aim 2. With the addition of raw ECG waveforms electronic health record information to pre-existing data in our pipeline, we aim to improve the predictive capacity of our model and potentially identify novel clinical associations for ATTR-CA.

2.9. Orthopedic manifestations: Previous work has shown that the orthopedic manifestations of carpal tunnel syndrome,²² spinal stenosis,^{23, 24} and hip and knee osteoarthritis requiring arthroplasty²⁵ can precede the diagnosis of cardiac amyloidosis by up to 5-7 years. Pathophysiologically, the carpal tunnel and multiple areas in the spine are small, compressed spaces. As a result, relatively little amyloid deposition can lead to significant symptoms, and nerve involvement may accentuate pain syndromes. The period of time when patients have symptomatic carpal tunnel syndrome, spinal stenosis, or osteoarthritis but before they have developed symptomatic heart disease could be an ideal time to diagnose systemic amyloidosis and initiate treatment. Preliminary work at our institution using manual chart abstraction has demonstrated that these orthopedic manifestations are more common in ATTR-CA patients than in controls (to be presented at International Society of Amyloidosis 2020 meeting). In order to incorporate these features in our model, we will collect electronic health record data on orthopedic manifestations as documented by Diagnosis Related Group codes, past medical and surgical history, and problem lists all patients seen in the CUIMC system. We will then incorporate this data into our deep learning models with two significant goals: (1) assess improvement in model's capacity to detect ATTR-CA, and (2) determine if it is possible to develop a model which prioritizes detection of patients with earlier cardiac involvement.

2.10. Electrocardiogram waveform analysis: Our current deep learning model uses tabular ECG data from the MUSE system documenting stored voltages and deflections. We believe that improvements to the ECG portion of this model are possible by adding raw waveform data. The waveforms on a 12 lead ECG are feature-rich with ~50,000 discrete data points as opposed to ~700 data points that are stored in the tabular data. Prior work has shown that deep learning analysis of 12 lead ECGs can identify significant pathology that would be essentially invisible to a human interpreter.¹⁶ We plan to include the raw ECG waveform data in the NAC/NALU models as well as develop a convolutional neural network (CNN) model based primarily of the waveform data. The CNN model will be developed similarly using the same train/development/test splits previously discussed. We will utilize the Adam optimizer and binary cross entropy as the loss function. We will assess convolutions across a single lead as well as a pooled convolution across all leads. We will then evaluate performance characteristics of the model with probability thresholds of 1%, 5%, 10%, 20%, 50%, and 75%. By adding raw waveforms data, we aim to increase the AUC of our model to >0.90.

2.11. Testing for novel clinical associations by using deep learning: The most promising aspect of NAC/NALU-based deep learning models is that by learning generalizable numerical representations, there is hope to build neural networks that are explainable with simple and sparse arithmetic of raw input features. Compared to other deep learning models, the output is more interpretable and is essentially an equation. The addition of a Laplacian-regularized filter pushes the model to make values more binary, either including them entirely or not at all. Instead of finely tuning hundreds of knobs, the model is asked to flip on switches of fewer input variables that matter.

While this may sacrifice some overall performance, it pushes the model towards simplicity which we believe limits overfitting, improves generalizability, and most importantly points out fewer variables that actually matter. To be used in real clinical settings and also derive insight on novel clinical associations, a model incorporation thousands of variables is unlikely to be successful. With such restrictions in place, we seek to determine if there is at least one novel clinical association that is found to be important in detecting ATTR-CA that is not currently known in the scientific community.

2.12. Future Directions: (1) Clinical trial to detect early stage amyloidosis: Our initial clinical trial (Aim 1) will likely result in identification of patients with later stage cardiac amyloidosis. By adding the orthopedic manifestations and ECG waveform data and tuning the model for earlier stage disease (Aim 2), we hope to be able to repeat this clinical trial but target patients with earlier stage disease (2) Deployment of the model at additional centers: The use of ECG, echocardiographic, demographic data, and clinical diagnoses to identify cardiac amyloidosis is generalizable to other medical centers. We anticipate that this model could be used at other centers to identify further cohorts of patients with cardiac amyloidosis. (3) Application of this research model to other diseases: The use of artificial intelligence analysis of pre-existing clinical data to identify undiagnosed disease has significant potential outside of the study of amyloidosis. It is possible that training similar models targeted at other diseases could have success in increasing identification of rare disease such as primary pulmonary hypertension or diseases that have a latency period that allows for improved treatment with earlier initiation such as cancer.

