2.2 Rationale

This study aims to create an automated, end-to-end pathway which can accurately identify patients at high probability of having cardiac amyloidosis who are currently undetected. The specific analytical objectives of this aim include the following: (1) use a deep learning model to identify 100 patients at high probability of having undiagnosed cardiac amyloidosis and invite them for diagnostic testing with the hypothesis that $\geq 20\%$ will be found to have cardiac amyloidosis. A positive detection rate of this amount could likely allow for effective active case surveillance in at-risk populations and result in adoption of the technology at other institutions, potentially leading to thousands of additional diagnoses being made each year.

2.3. Database Structure:

Our informatics pipeline uses three major sources of data for this study: (1) a database of cardiac amyloidosis cases and controls, (2) an ECG database, and (3) an echocardiogram database (Figure). The cardiac amyloidosis cases and controls database includes 753 consecutive patients who underwent 99mTc-PYP scanning. Using this database, we identified 212 patients with definite ATTR-CA by consensus criteria and 455 patients with no cardiac amyloidosis.^{18, 19} A manuscript analyzing these patients in detail is in revisions. Additional lists of patients with AL-CA and ATTR-CA were obtained from department records. The ECG database includes over 2 million ECGs. At Columbia University Irving Medical Center, ECGs are stored and analyzed digitally using the MUSE Cardiology Information System (GE Healthcare, Chicago, IL, United States). For each individual ECG, the MUSE database stores high level, quantitative data in a matrix format for all 12 ECG leads in addition to the physician text-based report. Quantitative data includes interval length (such as PR,

[figure not shown]

Figure 2. Visual representation of database information. Our database has three significant inputs (ECG, abstracted clinical information, and echocardiography) which are used in our deep learning model to predict one output (presence or absence of ATTR-CA, typically as diagnosed by 99mTc-PYP scanning).

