2.3.3 Hypotheses

Specific Aim 1: To prospectively validate that deep learning models can detect undiagnosed cardiac amyloidosis in large populations of patients undergoing cardiac testing

The specific hypothesis is that by applying an cardiac amyloidosis deep learning detection model to the entire Columbia database of patients, we will identify a group of patients at highest likelihood of having undiagnosed cardiac amyloidosis. We will validate the model by prospectively scanning 100 subjects with cardiac amyloid scintigraphy with $\geq 20\%$ being diagnosed with cardiac amyloidosis, a percentage that would potentially allow a cost-effective, wide-scale screening approach. The prevalence of cardiac amyloidosis in an unselected population of older adults who have undergone cardiac testing with an echocardiogram and ECG is unknown but is likely significantly less than 15% based on studies of more selected populations such as older adults with heart failure⁵ and aortic stenosis.³⁸ Based on our model's ability to accurately distinguish between cardiac amyloidosis cases and normal patients in a cohort of patients undergoing cardiac amyloid scintigraphy scanning, we predict that $\geq 20\%$ of patients identified by the model as being of high probability of having cardiac amyloidosis will be diagnosed with cardiac amyloidosis.

Specific Aim 2: To incorporate additional data to improve the deep learning model's detection of cardiac amyloidosis.

Hypothesis 1: Incorporating raw ECG waveform data and clinical variables such as orthopedic manifestations, e.g. carpal tunnel syndrome and spinal stenosis, associated with ATTR-CA, will improve the model's predictive capacity by 5% compared to currently used data in Aim 1.

Hypothesis 2: These deep learning models will allow identification of at least one key variable not currently associated with ATTR-CA that can inform future amyloidosis research.

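### Section 2.9 sets no index date for the orthopedic predictors, so entries made during or after the amyloid work-up can enter the Aim 2 features and bias the gain tested in Hypothesis 1

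*Combined protocol and SAP*

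**What the plan says.** Section 2.9 (Orthopedic manifestations) names three record types as the source of the new predictors: "we will collect electronic health record data on orthopedic manifestations as documented by Diagnosis Related Group codes, past medical and surgical history", and problem lists. The data cover "past medical and surgical history, and problem lists all patients seen in the CUIMC system". No look-back window is given, and nothing requires an entry to precede the scan or the diagnosis. The same section justifies the predictors by evidence that these conditions can come up to 5-7 years before the diagnosis, and gives earlier detection as one of its two goals.

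The predictors feed Aim 2, Hypothesis 1 (section 2.3.3), which states that "Incorporating raw ECG waveform data and clinical variables such as orthopedic manifestations" and related variables "will improve the model's predictive capacity by 5% compared to currently used data in Aim 1".

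The labelled data are described under Database Structure. The cohort "includes 753 consecutive patients who underwent 99mTc-PYP scanning", and from it "we identified 212 patients with definite ATTR-CA by consensus criteria and 455 patients with no cardiac amyloidosis". The section adds: "Additional lists of patients with AL-CA and ATTR-CA were obtained from department records".

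The data are split 70/15/15 by patient, with 5-fold cross-validation (Traditional statistical modeling). The trial excludes anyone already tested for cardiac amyloidosis (synopsis, exclusion criterion 4; section 2.3.1).

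**The concern.** Past history and problem lists build up over time. If they are read as they stand on the day of the data pull, a labelled patient's features can include conditions first written down because amyloidosis was suspected or found. A candidate in the target population has never been tested and cannot have entries of that kind. The model would then be trained and evaluated on a kind of record that is absent where it is meant to be used.

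The planned internal validation would not show this. Splitting by patient keeps one person's data out of two sets, but late entries occur in training, development and test patients alike, and cross-validation shares the problem.

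What is at stake is the Hypothesis 1 estimate, and with it the case for the later trial in earlier-stage disease that section 2.12 hopes to build on the Aim 2 model.

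**Working it through.** **1. Is there a date rule anywhere?** Section 2.9 has none. The informatics pipeline (1.7), Database Structure, the two modeling sections and the waveform section (2.10) describe sources, splits and models without dating predictors against the work-up. The Aim 2 figure text raises temporal symptom patterns only as a question.

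**2. Can the plan's 5% be reproduced?** No. Hypothesis 1 gives no metric, no baseline and no absolute or relative scale, and it covers waveform and clinical variables together. Section 2.10 says "we aim to increase the AUC of our model to >0.90", but that is tied to waveform data and also lacks a baseline. Read as AUC with an assumed baseline of 0.80-0.90, 5% is 0.05 on the absolute scale, or 0.05 × 0.80 = 0.040 to 0.05 × 0.90 = 0.045 on the relative scale.

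**3. Illustration of size. All rates are assumptions.**
- Baseline score: binormal with AUC A, so d = √2·Φ⁻¹(A).
- One yes/no orthopedic flag, independent of the score given disease status, with prevalence p1 in cases and p0 in controls.
- Before work-up: p1 = 0.35, p0 = 0.20. Late entries raise p1 to 0.45 or 0.55 and leave p0 unchanged.
- Score and flag are combined by likelihood ratio. With c = ln(p1/p0) − ln[(1−p1)/(1−p0)]:

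AUC = A·[p1·p0 + (1−p1)(1−p0)] + p1(1−p0)·Φ[(d²+c)/(d√2)] + (1−p1)p0·Φ[(d²−c)/(d√2)]

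Worked case, A = 0.85 (d = 1.466):
- p1 = 0.35: c = 0.767; AUC = 0.59 × 0.85 + 0.28 × 0.9202 + 0.13 × 0.7474 = 0.8563, a gain of 0.0063.
- p1 = 0.45: c = 1.186; AUC = 0.53 × 0.85 + 0.36 × 0.9461 + 0.11 × 0.6788 = 0.8658, a gain of 0.0158.
- Overstatement: 0.0158 − 0.0063 = 0.0095.

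| Baseline AUC | Gain, pre-work-up entries only | Gain, +10 points in cases | Gain, +20 points in cases | Overstatement, +10 | Overstatement, +20 |
|---|---|---|---|---|---|
| 0.80 | 0.0093 | 0.0230 | 0.0410 | 0.0137 | 0.0317 |
| 0.85 | 0.0063 | 0.0158 | 0.0284 | 0.0095 | 0.0220 |
| 0.90 | 0.0039 | 0.0097 | 0.0175 | 0.0058 | 0.0137 |

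(Overstatements are taken before rounding.)

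**4. Against the target.** On the absolute scale, the overstatement is 0.0058/0.05 = 12% to 0.0137/0.05 = 27% of the target with +10 points, and 27% to 0.0317/0.05 = 63% with +20 points. The largest share on the relative scale is 0.0317/0.040 = 79%. In that cell (baseline 0.80, +20 points) the apparent gain of 0.041 would just pass a relative 5%, although only 0.009 of it is genuine.

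**5. The other direction.** If late recording adds 10 points to both groups (45% against 30%), the gain at baseline 0.85 falls from 0.0063 to 0.0054.

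**The case against.** The best defense is that the plan is silent on timing and nowhere says that later entries will be used. Its rationale and its earlier-detection goal both point toward pre-diagnosis data. Aim 2 is model development, and any use of the resulting model is placed under future directions. This stands as a limit on the claim: the leak is a risk left open, not a documented fact. It does not remove the gap, because the section can be followed to the letter with every late entry included.

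Four stronger readings are tempting, and the documents do not support them.

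- **That the bias must be upward.** The 455 controls come from the same scanned cohort as the 212 cases, so they were worked up too. Nothing says that orthopedic history is sought or recorded more often after a positive result. Fuller recording in cases is plausible, but equal recording would dilute the gain.
- **That the department lists make it worse.** The text says only that the lists were obtained. It does not say whether those patients are used to train or test the Aim 2 models.
- **That the leak alone matches the 5%.** For the flag used alone, AUC = 0.5 + (p1 − p0)/2 gives 0.575, 0.625 and 0.675, a rise of 0.05-0.10. Hypothesis 1 concerns the change in a full model, where the same rates give 0.006-0.032.
- **That the whole record is searched.** Three record types are named.

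The objection that a date cut costs data also stands. It could remove many undated past-history and problem-list entries, and the documents do not show that order or first-mention dates are already held in the pipeline.

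**Conclusion.** The point holds as a gap in the design of Aim 2. The plan justifies the orthopedic predictors by their timing but does not restrict them by time, and its validation scheme cannot detect the consequence. The direction of bias depends on whether late entries are commoner in cases than in scanned controls, which the documents do not settle.

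Under the assumed rates, with late entries in cases only, one flag overstates the full-model AUC gain by about 0.006-0.014 (+10 points) or 0.014-0.032 (+20 points). That is a material part of the 5% sought rather than the whole. The figures rest on assumed prevalences, an assumed baseline AUC of 0.80-0.90, a binormal score and a conditionally independent flag. Several flags recorded separately could add to more than one flag does, and flags recorded together would add less; no size is claimed for that.

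A reader might infer that the trial's main result is at risk. It is not: the Aim 1 hypothesis of at least 20% diagnosed among 100 participants is unaffected.

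**What to change.** In section 2.9, define an index date for every case and control and apply the same rule to both.

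- Use only orthopedic and other EHR clinical entries dated before the first amyloid work-up, meaning the scan or its order.
- For any department-list cases used, take the first recorded mention of amyloidosis as the index date.
- Test Hypothesis 1 on these features.
- Report the version with undated or later entries only as a sensitivity analysis.

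The cost is a date filter in the data pull, some work to establish the index dates, and a few sentences in section 2.9. The downside is real: some true earlier history first written down at the work-up would be lost, as would some undated problem-list or past-history entries, so the measured gain may be smaller.

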QRS, and QT intervals) and peak wave amplitude (such as P, Q, R, S, and T wave amplitude), and each lead can be analyzed individually or as a sum of all 12 leads. The echocardiogram database includes over 200,000 echocardiograms in more than 100,000 patients. At CUIMC, echocardiograms are stored digitally and analyzed using the Syngo system (Siemens Healthineers, Erlangen, Germany). Our echocardiogram database contains abstracted information from the clinician report, including interventricular septal thickness, LV posterior wall thickness, LV ejection fraction, LV end-diastolic dimension, left atrial volume indexed for body surface area, and aortic root dimensions. With the combination of these three databases, we are able to rapidly conduct experiments to identify ECG, echocardiographic, demographic, and clinical features which distinguish ATTR-CA cases from normal controls.

4.12. Traditional statistical modeling:

The dataset used to create the traditional statistical model has nearly 1,000 variables per individual case. To ensure all cases are included, they must have <10% of data missing including no missing data in variables considered most critical (LV ejection fraction, interventricular septal thickness, posterior wall thickness, age, gender, ECG paced versus unpaced). From there, multiple imputation by chained equations (MICE) is conducted to ensure all cases are included. Data is then separated into training (70%), development (15%), and test (15%) data sets on a per-patient level. Due to limited size of the dataset, 5-fold cross-validation will be utilized. To deal with the high dimensionality of the data, both logit and probit regression models are generated. To minimize overfitting we prefer the use of L1 regularization over L2.

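### Aim 2, Hypothesis 2 can be met by a chance variable, because the plan sets no error rate for a single selected variable and has no step that confirms it

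*Combined protocol and SAP*

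**What the plan says.** Section 2.3.3 gives Hypothesis 2 of Aim 2 as: "These deep learning models will allow identification of at least one key variable not currently associated with ATTR-CA". The sentence then presents the variable as input to later research in the field. Section 2.11 puts the same goal as "With such restrictions in place, we seek to determine if there is at least one novel clinical association that is found to be important", with the added condition that the association is unknown so far. Neither section defines important or key, and no list of known associations is given.

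The pool is large. Under Traditional statistical modeling (numbered 4.12), the dataset "has nearly 1,000 variables per individual case", and the deep learning models use the same data and split. Sections 2.9 and 2.10 add orthopedic record data and raw ECG waveforms. The Figure 4 caption says the team hopes to "potentially identify novel clinical associations for ATTR-CA".

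Selection rests on sparsity. Section 2.11 says the Laplacian regularization "pushes the model to make values more binary, either including them entirely or not at all", and that the push towards simplicity "most importantly points out fewer variables that actually matter". The strength of the prior is not stated. Data are split 70/15/15 by patient, with "patients identically coded into those groups to allow for direct comparison". Five-fold cross-validation is used, and model performance is evaluated at set probability thresholds.

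**The concern.** A numbered hypothesis with a count in it will be reported as met or not met. Here one variable is enough, it comes from a very large pool, and the plan relies on sparsity to separate signal from noise. Sparsity reduces how many variables are kept. It does not say how often a kept variable is noise. A team following the plan exactly could report a chance variable as a discovery and send later amyloidosis research after it, and the result would not show whether that had happened.

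**Working it through.** The plan gives no alpha, power, importance cut-off or sample size for Hypothesis 2, so there is no stated figure to reproduce.

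**1. What each safeguard does for a single variable**

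| Safeguard | Where | Purpose | Effect on one selected variable |
|---|---|---|---|
| Laplace prior | Deep learning model development; 2.11 | Fewer inputs, less overfitting | Real restraint, but no stated strength or error rate |
| 70/15/15 split | Traditional statistical modeling; Deep learning model development; 2.10 | Build models, compare them, evaluate performance | No test of a chosen variable is assigned to it |
| 5-fold cross-validation | Traditional statistical modeling | Model building with limited data | None |
| AUC target above 0.90 | 2.10 | Overall discrimination | A good AUC does not show that each retained input is real |
| Future directions | 2.12 | Repeat trial, other centers, other diseases | No replication of a selected variable |

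**2. Why an unstated rate matters**

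If each of m unrelated inputs were independently called important with probability a, the chance of at least one would be 1 - (1 - a)^m. With m = 1,000:
- a = 0.001 gives 63%
- a = 0.0001 gives 9.5%
- a = 0.05/1,000 = 0.00005 gives 4.9%

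The plan gives no a, so these values are assumptions. They show only how small the rate must be.

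**3. Illustrative selection simulation**

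Inputs from 2.3 Database Structure: 212 + 455 = 667 classified scan patients; 212/667 = 32% cases; 70% of 667 = 467 training patients. Assumed: pools of 200, 1,000 or 3,000 inputs; 5 or 10 real predictors; best-possible AUC 0.76 to 0.93; penalty chosen by 5-fold cross-validation (minimum loss or one standard error); 100 runs per setting.

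| Rule for counting a variable as important | Runs with at least one noise variable |
|---|---|
| Greedy model with weights -1, 0 or +1 | 0-33% |
| L1 logistic, at least half the largest coefficient | 0-28% |
| L1 logistic, at least a quarter of the largest | 2-92% |
| L1 logistic, any non-zero coefficient | 83-100% (60% in one setting when the one-standard-error penalty was coded differently) |

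- In the first row, the rate was 6-33% when every real predictor had log-odds 0.5 per SD, and 0-8% when they were stronger or of mixed strength.
- With blocks of 12 inputs correlated at 0.7, the first row gave 1-4% and the last 90-100%.
- With no real predictor among 1,000 inputs, the last rule gave 16-35%. This is outside the table's ranges.
- The Monte Carlo standard error at 33% is sqrt(0.33 x 0.67/100) = 4.7 points.

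**4. Confirming nominees in the test set**

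If only the 667 are used, the test set has 15% of 667 = 100 patients and 15% of 212 = 32 cases. Nominees come from the other 85% (567 patients, held fixed throughout). There are five nominees, so the first Holm step is 0.05/5 = 0.01. Each is tested by likelihood ratio, adjusted for a known-predictor score, with the same direction required (200 runs per setting). Other assumed totals were 500 and 1,000 patients, giving test sets of 75 and 150.

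| Odds ratio per SD of one true novel variable | Power, test n = 75 | n = 100 | n = 150 |
|---|---|---|---|
| 1.65 (log-odds 0.5) | 11-13% | 20-21% | 24-35% |
| 2.0 (log-odds 0.7) | 32-36% | 41-52% | 67-69% |
| 2.7 (log-odds 1.0) | 67-69% | 80-85% | 95-98% |

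With no true novel variable, a noise variable passed in 3.0-4.5% of runs.

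**5. Would later scan patients add power?**

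Section 2.3 gives 667/753 = 0.886 classifiable, so 100 such patients need 100/0.886 = 113 scans. At the 2019 volume in section 1.5 (more than 130 a year), that is at most 113/130 x 12 = 10.4 months. Power at an odds ratio of 1.65 would be about 18-29%, close to the test set's 20-21%. About 80% power (77-83%) needs roughly 350 classifiable patients: 350/0.886 = 395 scans, and 395/130 = 3.0 years.

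**The case against.** The strongest reply is that this aim is exploratory. The Figure 4 caption says only "potentially identify novel clinical associations for ATTR-CA", section 2.11 frames the goal as something to be determined, and Hypothesis 2 offers its variable as material for later research. No alpha, endpoint or clinical decision depends on it. The prior, the splits and cross-validation are real restraints. A strict confirmation rule would miss about 80% of true novel variables at an odds ratio of 1.65, which is a heavy price for a discovery aim.

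Much of this stands. The aim is partly described as a source of leads, and the low power is real. That is why relabelling is an acceptable fix. It does not remove the point: section 2.3.3 still predicts that at least one variable will be identified, and none of the restraints tells a reader how likely that variable is to be noise.

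It is also fair that no simulation here reproduces LR-NAC or LR-NALU. The highest rates belong to L1 logistic regression under the loosest reading of important. L1 is named for the traditional logit and probit models, whereas Hypothesis 2 concerns the deep learning models, whose weights are driven towards -1, 0 or 1.

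**Conclusion.** The point holds and should be settled before the Aim 2 run. As written, a chance variable can meet Hypothesis 2, and the plan gives no means of knowing how often. The closer illustrative model puts this at 0-33% of runs, and looser importance rules put it far higher. These figures rest on simulated inputs, assumed effect sizes and a training set of 467, which assumes that only the 667 classified scan patients are used. Section 2.3 also mentions extra case lists of unstated size, and Traditional statistical modeling applies a missing-data rule.

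A reader might infer more than the documents support:
- **That chance will almost always meet the hypothesis.** That describes L1 regression with any non-zero coefficient, not the planned layers.
- **That LR-NAC and LR-NALU are rival models with no rule for choosing between them.** The plan introduces them as layers.
- **That diagnoses, symptom patterns and vital signs are confirmed new inputs.** The figure text near 2.8, "New diagnosis associations? Predictive temporal symptom patterns? Suggestive vital sign patterns", is a set of questions from a figure not shown, and may describe outputs sought. Added record and waveform data are confirmed by the Figure 4 caption, 2.9 and 2.10.
- **That the trial's main result is at risk.** Aim 1 rests on the share diagnosed among 100 scanned patients and is untouched.

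**What to change.** Amend section 2.11 and Hypothesis 2 along these lines:

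> Before the Aim 2 run we fix the list of known associations, the final model, the importance metric and a small maximum number of nominees (for example 5). Nominees are chosen in the training and development data only. Each is tested once in the 15% test set, adjusted for a known-predictor score fitted in the training and development data, with the same direction required and Holm correction at 5%. Hypothesis 2 is met only if a nominee passes. Otherwise the selected variables are reported as hypothesis-generating candidates.

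This costs one paragraph and a fixed list, with no new patients. The downside is low power for modest effects.

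If the sponsor judges that power too low, or the test set has already guided variable choice, drop the success criterion and label Hypothesis 2 hypothesis-generating. That costs one sentence. Confirmation in 100 later scan patients should not be offered as a cure for low power, because it gives about the same power as the test set.
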